7.1.3. Follow-up visit and early withdrawal* procedures list

*for early withdrawal, follow Day 85 procedures, then schedule a follow up visit.

7.2. Screening and Critical Baseline Assessments

Cardiovascular medical history/risk factors (as detailed in the eCRF) will be assessed at screening.

The following demographic parameters will be captured: year of birth, sex, race and ethnicity.

Medical/medication/family history will be assessed as related to the inclusion/exclusion criteria listed in Section [5](#).

Starting at Screening Day 1, subjects will complete the daily pain NRS questionnaire (2 questions, approx. 1-2 minutes, see [Appendix 8](#) and [Appendix 9](#)), for at least 7 days to determine their eligibility to participate in the study. Subjects will complete their first and all subsequent pain NRS questionnaires at home, at approximately the same time each day (recommended between 6pm-10pm). Once lab screening results are available and after completion of at least 7 consecutive days of pain NRS questionnaires, the subject's eligibility to continue to participate in screening (and progress to MRI scan) will be determined.

Eligibility is based on the '24h Average Pain NRS' question (see [Appendix 8](#)), taken over 7 consecutive days prior to the assessment. The average of the pain intensity scores over these 7 days is assessed, and an average of '5' or higher (on the 0-10 NRS), is required in order for the subject to be eligible to continue in screening.

If only one hand is affected by HOA and meets the inclusion criteria, the affected hand will be documented at screening and used for all assessments. In cases where both hands are affected by HOA **and both meet the inclusion criteria**, then the dominant hand will be documented at screening and this hand will be used for all MRI assessments throughout the study.

MRI of the affected hand will take place only if the subject has passed all other screening assessments, including all lab assessments and the Pain NRS 7-day assessment. MRI will be the final screening assessment.

All subjects should continue to complete the daily pain NRS questionnaire until all their screening assessments (including MRI) are completed and the final outcome on whether they can participate in the study has been determined. If the subject passes screening and is able to participate in the study, they should continue to complete their daily pain NRS questionnaires until the Week 12 visit has been completed. A final 7 day period of pain NRS questionnaires will then take place in the week prior to the follow-up visit at Week 22.

7.3. Efficacy

Patient Reported Outcomes questionnaires should be completed by subjects before any other assessment at a clinic visit, in the order specified at the start of Section [7](#).

Efficacy assessments will be performed at the time points presented in the Time and Events Table (Section 7.1).

Efficacy assessments will include evaluation of hand pain (Pain NRS questionnaire), hand function, pain on use and stiffness (AUSCAN 3.1 NRS), disease activity (patient and physician global assessment of disease activity, PtGA/PhGA), and number of tender, and swollen joints in their hands. For pain efficacy assessments the average pain intensity over 7 days prior to the assessment date will be used. This is calculated from collected daily pain NRS data over the 7 day period prior to the study visit.

7.3.1. Subject's Assessment of Hand Pain, Function, Stiffness, and Subject's / Clinician's Assessment of Global Disease Activity

The patient reported outcome (PRO) questionnaires (Pain NRS, AUSCAN 3.1 NRS, Patient Global Assessment of Disease Activity [PtGA]) will be completed at relevant study visits or at home as described in the Time and Events Table (Section 7.1), and the data entered into the eCRF.

Pain intensity will be assessed by subjects, at home, using a daily Pain NRS (0-10) questionnaire. Subjects will record their 'average hand pain' and 'worst hand pain' intensity over the past 24 hours (see [Appendix 8](#) and [Appendix 9](#)), they will also record any use of any rescue paracetamol (acetaminophen) for hand pain over the past 24 hours. This should take place at approximately the same time each day (recommended between 6pm-10pm) for the 12-week treatment period of the study.

Hand function, pain on use and stiffness will be assessed using the AUSCAN Index. Patients will complete the AUSCAN 3.1 NRS at study visits.

A global assessment of disease activity will be completed by subjects and clinicians using a Patient Global / Physician Global Assessment of Disease Activity (PtGA/PhGA) item, which asks subjects / clinicians to rate the level of disease activity today on an 11-point Numeric Rating Scale (NRS, 0-10) with anchors 'Very well' and 'Very Poor' for the PtGA, and anchors 'None' and 'Extremely Active' for the PhGA.

Joint Assessments

To prevent potential bias because of observed efficacy changes, the Joint Assessor must not be the treating physician (PI or sub-investigator) or the unblinded drug administrator.

The Joint Assessor (or designee) should be a rheumatologist or other skilled arthritis assessor and will be responsible only for completing the joint counts. To ensure consistent joint evaluation throughout the trial, individual subjects should preferably be evaluated by the same joint assessor for all study visits.

Treating Physician

The Treating Physician (or designee) should be a rheumatologist (or other medically qualified physician) and will have access to both safety and efficacy data. The Treating

Physician will have access to source documents, laboratory results and eCRFs and will be responsible for completing Physician's Global Assessment of Disease Activity, and safety assessments (adverse events, vital signs, concomitant medications, and review of laboratory data).

It is essential that assessments completed by the subject and Joint Assessor are made before those by the Treating Physician.

7.4. Safety

Planned time points for all safety assessments are listed in the Time and Events Table (Section 7.1). Additional time points for safety tests such as vital signs, physical exams and laboratory safety tests may be added during the course of the study based on newly available data to ensure appropriate safety monitoring.

7.4.1. Adverse Events (AE) and Serious Adverse Events (SAEs)

The definitions of an AE or SAE can be found in [Appendix 4](#).

The investigator and their designees are responsible for detecting, documenting and reporting events that meet the definition of an AE or SAE.

7.4.1.1. Time period and Frequency for collecting AE and SAE information

- Any SAEs assessed as related to study participation (e.g., protocol-mandated procedures, invasive tests, or change in existing therapy) or related to a GSK product will be recorded from the time a subject consents to participate in the study up to and including any follow-up contact.
- AEs will be collected from the start of Study Treatment until the follow-up contact (see Section 7.4.1.3), at the time points specified in the Time and Events Table (Section 7.1).
- Medical occurrences that begin prior to the start of study treatment but after obtaining informed consent may be recorded on the Medical History/Current Medical Conditions section of the eCRF.
- All SAEs will be recorded and reported to GSK within 24 hours, as indicated in [Appendix 4](#).
- Investigators are not obligated to actively seek AEs or SAEs in former study subjects. However, if the investigator learns of any SAE, including a death, at any time after a subject has been discharged from the study, and he/she considers the event reasonably related to the study treatment or study participation, the investigator must promptly notify GSK.

NOTE: The method of recording, evaluating and assessing causality of AEs and SAEs plus procedures for completing and transmitting SAE reports to GSK are provided in [Appendix 4](#).

7.4.1.2. Method of Detecting AEs and SAEs

Care will be taken not to introduce bias when detecting AEs and/or SAEs. Open-ended and non-leading verbal questioning of the subject is the preferred method to inquire about AE occurrence. Appropriate questions include:

- “How are you feeling?”
- “Have you had any (other) medical problems since your last visit/contact?”
- “Have you taken any new medicines, other than those provided in this study, since your last visit/contact?”

7.4.1.3. Follow-up of AEs and SAEs

After the initial AE/SAE report, the investigator is required to proactively follow each subject at subsequent visits/contacts. All SAEs, and non-serious AEs of special interest (as defined in Section 7.4.2) will be followed until resolution, until the condition stabilizes, until the event is otherwise explained, or until the subject is lost to follow-up (as defined in Section 5.4). Further information on follow-up procedures is given in [Appendix 4](#).

7.4.1.4. Cardiovascular and Death Events

For any cardiovascular events detailed in Section 12.4.3 and all deaths, whether or not they are considered SAEs, specific Cardiovascular (CV) and Death sections of the CRF will be required to be completed. These sections include questions regarding cardiovascular (including sudden cardiac death) and non-cardiovascular death.

The CV CRFs are presented as queries in response to reporting of certain CV Medical dictionary for regulatory activities (MedDRA) terms. The CV information should be recorded in the specific cardiovascular section of the CRF within one week of receipt of a CV Event data query prompting its completion.

The Death CRF is provided immediately after the occurrence or outcome of death is reported. Initial and follow-up reports regarding death must be completed within one week of when the death is reported.

7.4.1.5. Regulatory Reporting Requirements for SAEs

Prompt notification by the investigator to GSK of SAEs related to study treatment (even for non- interventional post-marketing studies) is essential so that legal obligations and ethical responsibilities towards the safety of subjects and the safety of a product under clinical investigation are met.

GSK has a legal responsibility to notify both the local regulatory authority and other regulatory agencies about the safety of a product under clinical investigation. GSK will comply with country specific regulatory requirements relating to safety reporting to the regulatory authority, Institutional Review Board (IRB)/Independent Ethics Committee (IEC) and investigators.

Investigator safety reports are prepared for suspected unexpected serious adverse reactions according to local regulatory requirements and GSK policy and are forwarded to investigators as necessary.

An investigator who receives an investigator safety report describing a SAE(s) or other specific safety information (e.g., summary or listing of SAEs) from GSK will file it with the IB and will notify the IRB/IEC, if appropriate according to local requirements.

7.4.2. AEs of Special Interest (AESIs)

Please see Section [4.7.1](#) for a discussion of potential risks with GSK3196165. Adverse events of special interest include:

- Serious infections, including serious respiratory infections and tuberculosis.
- Opportunistic infections.
- Neutropenia
- Respiratory events including
 - Pulmonary alveolar proteinosis (PAP).
 - Persistent (for 3 consecutive weeks) reduction in $D_{LCO} > 15\%$
 - Persistent (for 3 consecutive weeks) cough and/or dyspnea
 - Non life-threatening pulmonary changes related to surfactant accumulation
- Hypersensitivity reactions including anaphylaxis.
- Injection site reactions

7.4.3. Pregnancy

- Details of all pregnancies in female subjects and female partners of male subjects will be collected after the start of dosing and until completion of the follow up visit at Week 22.
- If a pregnancy is reported then the investigator should inform GSK within 2 weeks of learning of the pregnancy and should follow the procedures outlined in [Appendix 5](#).

7.4.4. Physical Exams

- A complete physical examination will include, at a minimum, assessment of the Cardiovascular, Respiratory, Gastrointestinal and Neurological systems. Height and weight will also be measured and recorded.
- A brief physical examination will include, at a minimum assessments of the lungs, cardiovascular system, and abdomen (liver and spleen).
- Investigators should pay special attention to clinical signs related to previous serious illnesses

7.4.5. Vital Signs

- Vital signs will be measured in semi-supine position after 5 minutes rest and will include temperature, systolic and diastolic blood pressure and pulse rate.
- Three readings of blood pressure and pulse rate will be taken:
 - First reading should be rejected
 - Second and third readings should be recorded in the eCRF.

7.4.6. Electrocardiogram (ECG)

- Triplicate 12-lead ECGs will be obtained at each time point during the study using an ECG machine that automatically calculates the heart rate and measures PR, QRS, QT, and QTc intervals (based on averaged QTc values of triplicate electrocardiograms obtained over a brief, e.g. 5-10 minute, recording period). Refer to Section 5.4.2 for QTc withdrawal criteria and additional QTc readings that may be necessary.

7.4.7. Pulmonary Assessments

Pulmonary assessments are a key aspect of the safety monitoring in this study (refer to Section 5.5.1).

The following pulmonary assessments will be performed at the time points presented in the Time and Events Table (Section 7.1)

- Cough (See [Appendix 7](#)).
- Borg CR10 Scale (See SRM for details).
- Lung auscultation.
- Pulse oximetry.
- Pulmonary function tests (PFTs - spirometry, gas transfer [D_{LCO}]).

PFTs will be performed by individual sites. As a general guidance, sites are asked to follow the ATS/ERS recommendations for lung function testing [[Miller](#), 2005a; [Miller](#), 2005b; [Macintyre](#), 2005]. Spirometry should be performed prior to D_{LCO} . Subjects should avoid the following activities prior to undergoing the PFTs:

- Smoking within at least 1 hour of testing
- Consuming alcohol within 4 hours of testing
- Use of bronchodilators within 4 hours of testing
- Performing vigorous exercise within 30 minutes of testing
- Wearing clothing that substantially restricts full chest and abdominal expansion
- Eating a large meal within 2 hours of testing

7.4.8. Immunogenicity

GSK3196165 is a humanized monoclonal antibody that will be delivered by the subcutaneous route and is targeted to bind and neutralize a soluble target, and for these reasons, is considered to be a relatively low risk of inducing adverse immune responses [FDA, 2014].

Serum samples will be collected and tested for presence of antibodies that bind to GSK3196165. Serum samples for testing anti-GSK3196165 antibodies will be collected as described in the Time and Events schedule (Section 7.1). The actual date and time of each blood sample collection will be recorded. Details of blood sample collection (including volume to be collected), processing, storage and shipping procedures are provided in the Central Laboratory Manual.

The timing and number of planned immunogenicity samples may be altered during the course of the study, based on newly-available data to ensure appropriate safety monitoring. In the event of a hypersensitivity reaction that is either 1) clinically-significant in the opinion of the investigator, or 2) leads to the subject withdrawing from the study, blood samples should be taken from the subject for immunogenicity testing, at the time of the event and again 12 weeks after. For subjects who prematurely withdraw from the study, immunogenicity testing will occur at withdrawal and at follow-up 12 weeks after last dose.

Serum will be tested for the presence of anti-GSK3196165 antibodies using the currently approved analytical methodology using a tiered testing schema: screening, confirmation and titration steps. The presence of treatment emergent anti-drug antibodies (ADA) will be determined using a GSK3196165 bridging style ADA assay with a bio-analytically determined cut point determined during assay validation. Samples taken after dosing with GSK3196165 that have a value at or above the cut-point will be considered treatment-emergent ADA-positive. These ADA positive samples will be further evaluated in a confirmatory assay, and confirmed positive samples will be further characterized by assessment of titer. Results of anti-GSK3196165 antibody testing will be reported at the end of the study and will include incidence and titer. The presence or absence of antibodies to GSK3196165 in dosed subjects will be analyzed, then summarized descriptively and/or graphically presented.

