| 
 To assess potential impact of GSK3196165 on disease activity in HOA, | 
 Change from baseline in patient global assessment (PtGA) and physician global assessment (PhGA) of disease activity at Week 6,12 and 22. |
| 
 To assess safety of GSK3196165 in HOA patients, over the study duration. | 
 Incidence of adverse events and serious adverse events. Incidence of infections. Incidence of pulmonary events (cough/dyspnea, PAP and DLCO). Immunogenicity. |
| 
 To assess population pharmacokinetics of GSK3196165 in HOA. | 
 Population pharmacokinetics endpoints such as CL/F, Vss/F, Ka. |
| Exploratory | |
| 
 To explore the potential impact of GSK3196165 on disease progression/modification in HOA, using MRI imaging. | 
 Change from baseline in synovitis in the affected hand*, as measured by DCE-MRI including the exchange rate (K^{trans}), interstitial volume (v_e), plasma volume (v_p), volume of synovitis, initial rate of enhancement (IRE), and maximum signal intensity enhancement (ME). Change from baseline in structural and inflammatory HOA features in the affected hand* (including synovitis, erosive damage, cysts, osteophytes, cartilage space loss, malalignment, and bone marrow lesions) as assessed by the OMERACT HOAMRIS scoring system Change from baseline in structural and inflammatory HOA features in the affected hand* (including synovitis, bone erosions, joint space width, and bone marrow edema) as assessed by the RAMRIQ scoring system. Change from baseline in bone shape as assessed by structural MRI of the affected hand*. |
| 
 The exploration of the relationship | 
 Relationship between concentration or PK |

| Objectives | Endpoints |
|--|---|
| between GSK3196165 PK and PD effects and/or efficacy. | parameters and PD endpoint(s). |
| 
 To evaluate the potential of GSK3196165 to affect biomarkers of HOA. | 
 Change in blood biomarkers from baseline at each visit. |

[figure not shown]

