4.4. Type and Number of Subjects

Approximately 40 subjects with active inflammatory HOA who have passed all screening assessments, will be enrolled onto the study. At least 40 subjects will be randomized across the two treatment arms, to either placebo or GSK3196165, in a 1:1 ratio (n=20 per arm).

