| | | 
Form.
 
 Should hypersensitivity or anaphylaxis occur, subjects should be managed appropriately per local guidelines/medical judgement. Severe or serious hypersensitivity or anaphylaxis are categorised as AESIs. 
Subject monitoring:
 
 Subjects should be monitored for hypersensitivity reactions throughout the study, and the information recorded in the eCRF. Any clinically-significant event should be reported as an AE. 
Withdrawal criteria:
 
 In the event of severe or serious hypersensitivity or anaphylaxis, study medication should be discontinued and the subject withdrawn from the study. |
| Injection site reactions | 
SC injections may be associated with local reactions (e.g., swelling, induration, pain).
 
Non-clinical & Clinical Data:
 
No macroscopic or microscopic changes indicative of local injection site reactions were observed following IV or SC administration.
 | 
Subject monitoring:
 
 Subjects should be monitored for injection site reactions throughout the study, and the information recorded in the eCRF. Injection sites will be rotated. Any clinically-significant event should be reported as an AE. |
| Immunogenicity | 
Pre-clinical Data
 
Anti-drug antibodies (ADAs) to GSK3196165 were detected in some monkeys and was associated with reduced serum levels of GSK3196165; ADA associated toxicity was not observed.
 
Clinical Data
 
In Study MSC1000, one healthy volunteer who received a single dose of 25 µg/kg developed an IgM ADA at Day 15, and in Study
 | 
Investigate Risk
 
 Samples (pre-and post-baseline) will be collected from all subjects during the study to assess development of anti drug antibodies and will be analyzed at the end of the study. In addition to scheduled immunogenicity assessments, “event-driven” testing will also be employed for those subjects that experience anaphylaxis, serious |

| Potential Risk of Clinical Significance | Summary of Data/Rationale for Risk | Mitigation Strategy |
|---|--|---|

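### Section 7.4.8 calls any post-dose sample at or above the assay cut-point treatment-emergent ADA-positive, whatever the subject's pre-dose result

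*Protocol*

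**What the plan says.** Section 7.4.8 (Immunogenicity) describes three tiers of testing: screening, confirmation and titration. Treatment-emergent ADA are to be determined with a "bridging style ADA assay with a bio-analytically determined cut point determined during assay validation". The rule follows: "Samples taken after dosing with GSK3196165 that have a value at or above the cut-point will be considered treatment-emergent ADA-positive". The next sentence gives the later tiers: "These ADA positive samples will be further evaluated in a confirmatory assay, and confirmed positive samples will be further characterized by assessment of titer".

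Two sentences cover reporting: "Results of anti-GSK3196165 antibody testing will be reported at the end of the study and will include incidence and titer", and "The presence or absence of antibodies to GSK3196165 in dosed subjects will be analyzed, then summarized descriptively and/or graphically presented". Neither says whether the incidence is of treatment-emergent ADA or of any ADA.

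The immunogenicity row of Section 4.7.1 (Risk Assessment) gives the purpose of sampling: "Samples (pre-and post-baseline) will be collected from all subjects during the study to assess development of anti drug antibodies". The Time and Events table in Section 7.1.2 marks an immunogenicity sample on Day 1. The synopsis and Section 3 list immunogenicity among the endpoints for the secondary safety objective.

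**The concern.** Treatment-emergent means that a finding appeared, or clearly increased, after treatment began. The rule tests only two things: that the sample was taken after dosing, and that its value reaches the cut-point. Neither shows when the reactivity began. The protocol collects the pre-dose sample that would show this, and then defines the label without using it.

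What is at stake is the descriptive immunogenicity result for the active arm. If its incidence is built on this label, reactivity that the drug did not cause is counted as induced by the drug. A sample taken because of a hypersensitivity event would receive the same label, and could suggest a drug-induced antibody where there was none. The efficacy analysis does not use ADA status.

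**Working it through.** The protocol states no ADA rate, so there is no figure of its own to reproduce. The check is first of the wording, then of the possible size.

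**Wording.** The rule applied to each pattern in a subject dosed with GSK3196165:

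| Pre-dose sample | Post-dose sample | Label under Section 7.4.8 | Emergent on treatment? |
|---|---|---|---|
| below cut-point | below cut-point | no | no |
| below cut-point | at or above | yes | yes, if confirmed |
| at or above | at or above, unchanged | **yes** | **no** |
| at or above | at or above, clear rise in titer | yes | yes, if confirmed |
| at or above | below cut-point | no | no |

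The third row is the error. The later tiers do not remove it:

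- *Cut-point.* It is set at assay validation, so it is the same for every subject and carries no information about that subject's baseline.
- *Confirmation.* This tests whether the reactivity is specific. Drug-specific antibody that was present before dosing would confirm again afterwards.
- *Titration.* Titer is measured on confirmed positives, but no comparison with a pre-dose titer is stated and no fold rise is given.
- *Order.* The label is attached at the screening tier. Read literally, a sample that later fails confirmation has already been called treatment-emergent ADA-positive.

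Sections 3, 4.7.1, 7.1.2, 9.4 and 9.4.3 add no pre-dose condition in the text available.

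**Possible size, if the reported incidence uses the label.** Inputs:

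- n = 20 active subjects (Section 4.4).
- p = proportion reactive before dosing. Not in the protocol; assumed 1%, 5% or 10%.
- s = fraction of those who are at or above the cut-point after dosing without a treatment-related rise. Not in the protocol; assumed 1 (upper bound) or 0.5.

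Formulas:

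- effect of one subject = 1/20 = 5 percentage points
- expected number mislabelled = 20 × p × s
- chance of at least one = 1 − (1 − p × s)^20

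| p | s | Expected of 20 | Chance of at least one |
|---|---|---|---|
| 1% | 1 | 20 × 0.01 = 0.2 | 1 − 0.99^20 = 18% |
| 5% | 1 | 20 × 0.05 = 1.0 | 1 − 0.95^20 = 64% |
| 10% | 1 | 20 × 0.10 = 2.0 | 1 − 0.90^20 = 88% |
| 1% | 0.5 | 20 × 0.005 = 0.1 | 1 − 0.995^20 = 10% |
| 5% | 0.5 | 20 × 0.025 = 0.5 | 1 − 0.975^20 = 40% |
| 10% | 0.5 | 20 × 0.05 = 1.0 | 1 − 0.95^20 = 64% |

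For scale, Section 4.7.1 reports one ADA case in study MSC-1001. With the 69 active subjects given in Section 2.2.4, that is 1/69 = 1.4%. One mislabelled subject here would be 5%.

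**The case against.** The strongest reply is that the sentence sorts samples within an assay procedure and does not define a subject-level endpoint. Neither reporting sentence uses the term treatment-emergent, and the endpoint tables say only that immunogenicity will be assessed. Sections 9.4 and 9.4.3 leave full details to the reporting and analysis plan, where the handling of baseline-positive subjects and the fold-rise threshold would normally be set. The stated aim of assessing development of antibodies implies a comparison with the pre-dose sample, so the wording may just be loose.

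Part of this stands. The protocol does not tie its reported incidence to the label, so the 5-point effect is conditional. The analysis plan, which was not available, may add a baseline condition. But the protocol does not leave the definition open: it states one, and that definition is wrong as written. An analysis plan that added a baseline condition would depart from Section 7.4.8.

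Two further points stand as limits. Note 5 to the Day 1 immunogenicity sample in Section 7.1.2 could not be read in the text available and should be checked, although Section 4.7.1 confirms that pre-baseline samples are taken. The rates of pre-existing reactivity have no basis in the protocol. Both earlier ADA cases in Section 4.7.1 are described as having developed after dosing, which neither supports nor excludes such rates. The rows with s = 1 are a ceiling, not an estimate.

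**Conclusion.** The concern holds. As written, the rule labels unchanged pre-existing reactivity as treatment-emergent, and nothing in the visible protocol corrects it. The effect is 5 percentage points per such subject among 20 on active treatment, provided that the reported incidence uses the label; otherwise no number changes. How many subjects would be affected is unknown, and the figures of 0.1 to 2.0 of 20 rest wholly on assumed rates. The rule reaches only samples taken after dosing with GSK3196165, so placebo subjects are not labelled. The primary analysis, power and withdrawal rules do not depend on ADA status. The point is minor.

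**What to change.** In Section 7.4.8, define a subject as treatment-emergent ADA-positive when a post-dose sample is confirmed positive and either the pre-dose sample is negative, or the titer has risen over a positive pre-dose sample by a pre-specified fold. Report baseline-positive subjects separately, and say whether the reported incidence is of treatment-emergent or of any ADA.

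The cost is one or two sentences for the definition and a clause for the reporting. The pre-dose samples and all three assay tiers are already planned. The text should also state that confirmed positive pre-dose samples will be titrated, since the fold rise cannot be computed without that.
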